IPV as a barrier to PMTCT adherence and retention: For my PhD dissertation and NIMH-funded F31 award, I led a mixed methods study in Zambia examining the relationship between gender power dynamics and HIV-positive women’s PMTCT adherence and retention. The results of this study indicate that HIV-positive pregnant and postpartum women in Zambia experience disproportionately high rates of IPV (>60%) compared to the general population of women.⁸ Moreover, women who experienced IPV, particularly emotional IPV, have reduced odds of adherence to ART during and after pregnancy,⁸ safe infant feeding,²⁷ and early infant HIV testing.¹⁸

Engaging men in PMTCT interventions: For my postdoctoral fellowship, I am leading a mixed methods study in western Kenya within the framework of my mentors' community randomized trial (R01HD0808477; PIs: [name], [name].). My sub-study examines the importance of specific male behaviors and relationship dynamics for PMTCT and ways to engage male partners in HIV care. The results from this research will help inform the specific content of the proposed K99/R00 couples counseling intervention.

IV. Research Methods

A. Outcome Measure(s):

The Primary outcome is the percent of female participants with HIV viral suppression (viral load <1,000 copies/mL) at 24 weeks postpartum between the intervention and control groups. The **Secondary outcomes** are the percent of female participants with HIV viral suppression (viral load <1,000 copies/mL) at 6 weeks postpartum; the percent of female participants reporting ART adherence (using validated instruments); facility birth; exclusive breastfeeding; pediatric HIV testing, diagnosis, and treatment uptake; and postpartum family planning between the intervention and control groups.

B. Description of Population to be Enrolled:

Couples are eligible if: female is <36 weeks pregnant (to have time to deliver at least one counseling visit during pregnancy); female is diagnosed as HIV-positive; both partners are >18 years of age and willing to participate; both partners live in the clinic catchment area and plan to reside there for at least six months; a long-term stable relationship (sleep under the same roof at least once a week) that has existed for ≥ 6 months; and no severe IPV in the past 6 months.⁶³

C. Study Design and Research Methods

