Couples counseling visit 3	Intervention couples	Love and support	
 ➤ Couple meets with a male-female pair of counselors ➤ 90-minute session focused on how couples can show love and support for one another

Data Collection: The following service utilization and PMTCT outcome data will be collected at baseline (pregnancy), 6 weeks postpartum, and 24 weeks postpartum: (1) women’s viral load testing (i.e., research-only blood draws at the University Teaching Hospital (UTH) laboratory); and (2) behavioral surveys.

Viral load testing (female participants only): we will collect research-only blood draws at baseline, 6 weeks postpartum (mid-line), and 24 weeks postpartum (end-line) to determine HIV treatment success via viral suppression (<1000 RNA copies/ml). Blood will be collected by health care workers at the UTH laboratory, which has an existing infrastructure capable of drawing blood and testing viral loads.

Behavioral questionnaires (all participants): We will administer face-to-face behavioral surveys to both female and male participants at baseline, 6 weeks postpartum (mid-line), and 24 weeks postpartum (end-line) to capture self-reported service utilization and PMTCT outcomes, hypothesized mediating variables (intrapersonal and interpersonal factors, including relationship dynamics), sociodemographic characteristics, and intervention experiences (if applicable). The surveys will be verbally administered to all enrolled WLWH (both control and intervention arms) and their male partners by trained Zambian research assistants in the local languages. Survey data will be entered on pre-programmed tablets using the REDCap (Research Electronic Data Capture) mobile application and sent to the secure host server at the University of Colorado Denver. REDCap is a secure, web-based application designed to support data capture for research studies, providing: 1) an intuitive interface for validated data entry; 2) audit trails for tracking data manipulation and export procedures; 3) automated export procedures for seamless data downloads to common statistical packages; and 4) procedures for importing data from external sources. Data can be entered and securely stored on the tablet and subsequently sent to the server upon internet connectivity, which makes its use ideal for low-resource settings.

D. Description, Risks and Justification of Procedures and Data Collection Tools:

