Aim 1: Compare service utilization and PMTCT outcome indicators in two study conditions	Primary outcome: female viral suppression at 24 weeks postpartum (<1000 RNA copies/ml)	Intermediate outcomes: 
 ➤ female viral suppression at 6 weeks postpartum ➤ female self-reported ART adherence (visual analog scale using 3-day, one-week, and one-month recall periods) ➤ facility birth ➤ exclusive breastfeeding to six months ➤ uptake of pediatric HIV testing (and treatment if positive) ➤ postpartum family planning 	Research-only blood draws (female partner), + Behavioral surveys	Independent t-tests and Pearson's chi-square tests; logistic regression models with generalized estimating equation; survival analysis with cumulative incidence across time, Kaplan-Meier curves, mixed-effects Cox proportional hazards models
Aim 2: Establish the effect of the	Intrapersonal mechanisms: 
 ➤ mental health 	Interpersonal mechanisms: 
 ➤ IPV past month ➤ Intimacy and trust 	Behavioral surveys	Mediation analysis with structural equation modeling

intervention on intra- and inter-personal mechanisms influencing PMTCT outcomes	
 ➤ self-esteem ➤ perceived stigma ➤ perceived partner acceptance 	
 ➤ Communication skills ➤ problem-solving skills ➤ joint decision-making ➤ Conflict resolution skills ➤ Relationship satisfaction ➤ Perceived social support ➤ Communal coping 		(SEM)
--	---	---	--	-------

2. Sample size calculation: Based on the primary outcome (viral load) and a projected 25% loss to follow-up (10% due to break-ups and 15% due to other causes), we require 238 total couples (119 couples per arm) to achieve the sample size target of 178. This target is based on a Pearson's chi-squared two-sample proportions test with a power of 0.80 and alpha of 0.05, assuming a delta of 0.20 at the 6-month follow-up between the intervention and control arms. Based on recent studies from the region,⁵⁸⁻⁶⁰ we estimate viral suppression at 6-months to be 55% in the control arm and 75% in the intervention arm. For the intermediate and mediating variables on the behavioral survey, the proposed sample size will enable us to detect a hazard ratio of 0.75, power of 0.80, and alpha of 0.05, using a two-sample comparison of survivor functions exponential test.

G. Summarize Knowledge to be Gained:

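### No primary analysis of 24-week suppression is named, and the unadjusted chi-square implied by the sizing leaves the planned baseline viral load unused

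*Combined protocol and SAP*

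**What the plan says.** Section IV.A defines a single binary endpoint: "The Primary outcome is the percent of female participants with HIV viral suppression (viral load <1,000 copies/mL) at 24 weeks postpartum".

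The Aim 1 row of the table in section IV.F lists that endpoint beside six intermediate outcomes, among them "female self-reported ART adherence (visual analog scale using 3-day, one-week, and one-month recall periods". All seven share one cell of methods. It opens with "Independent t-tests and Pearson's chi-square tests" and continues with "logistic regression models with generalized estimating equation; survival analysis with cumulative incidence across time, Kaplan-Meier curves, mixed-effects Cox proportional hazards models". The text of IV.F.1 describes data collection and software. It assigns no method to an outcome, names no covariates, and does not say which visits or contrast a GEE model would use.

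Section IV.F.2 comes closest to naming a test for the primary outcome: "This target is based on a Pearson's chi-squared two-sample proportions test with a power of 0.80 and alpha of 0.05". The difference to be detected is 20 points, from 55% suppressed under control to 75% under intervention. Its next calculation, for a hazard ratio of 0.75, concerns the intermediate and mediating survey variables.

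On viral load, section IV.C says: "we will collect research-only blood draws at baseline, 6 weeks postpartum (mid-line), and 24 weeks postpartum (end-line". The Procedures text places the baseline sample at the first group session. The design text has randomisation follow that session, by labelled envelopes, with no stratification mentioned.

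**The concern.** A trial with one binary primary outcome should say in advance which model gives its result. Here at least three analyses of suppression remain open: a chi-square at 24 weeks, a GEE arm effect averaged over visits, and a GEE contrast at 24 weeks. The averaged effect answers a different question from the 24-week comparison. If the choice is made after the data are seen, the 5% error rate is no longer assured.

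The second part is efficiency. Suppression during pregnancy is likely to predict suppression at 24 weeks postpartum. It is planned for every woman, yet no section puts it into the primary comparison. Because adjustment for a pre-randomisation covariate needs no extra participants or samples, leaving it out gives up power for no saving.

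**Working it through.** **1. Reproduce the stated size.** Inputs from IV.F.2: p1 = 0.55, p2 = 0.75, alpha 0.05 (taken as two-sided), power 0.80, equal allocation, 25% loss. The pooled formula without continuity correction is

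n per arm = [1.960 × √(2 × 0.65 × 0.35) + 0.842 × √(0.55 × 0.45 + 0.75 × 0.25)]² / 0.20²
= [1.960 × 0.6745 + 0.842 × 0.6595]² / 0.04 = 88.1, rounded up to 89.

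The total is 178, and 178 / 0.75 = 237.3, rounded up to 238. Both stated figures reproduce. Power at 89 per arm is 0.804. The calculation uses no baseline information.

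**2. Power with baseline adjustment.** The documents give neither the baseline suppression rate nor its association with the outcome. Assumptions: 50% or 65% suppressed at baseline; odds ratio between baseline and 24-week suppression of 3, 6, 12 or 20. Trials were simulated with 89 women per arm and marginal rates fixed at 55% and 75%. Each was analysed by chi-square and by logistic regression on arm and baseline suppression.

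| Assumed odds ratio | Chi-square power | Adjusted power |
|---|---|---|
| 3 | about 80% | about 83% |
| 6 | about 80% | 85-87% |
| 12 | about 80% | about 90% |
| 20 | about 80% | 92-93% |

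An analytic cross-check gives the same picture. If baseline and outcome have correlation φ, the variance is multiplied by about 1 − φ², so the effective n per arm is 89 / (1 − φ²):

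- φ = 0.3: 89 / 0.91 = 97.8, power 0.84
- φ = 0.4: 89 / 0.84 = 106.0, power 0.87
- φ = 0.5: 89 / 0.75 = 118.7, power 0.90

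**3. Does the choice of test change conclusions?** Under the design effect, the chi-square and the adjusted model fall on opposite sides of 5% in about 5-15% of simulated trials. The figure rises with the assumed odds ratio.

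**4. False positives from an open choice.** With 55% in both arms, each test alone rejects about 5% of the time. Counting a trial as positive if either rejects gives about 5-8%.

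Leaving an analysis over visits open adds to this. A separate null simulation assumed 55% at both postpartum visits and a 6-to-24-week correlation of 0.3 to 0.7. The 24-week test alone (Wald z) rejected in about 6% of trials. Allowing either that test or a two-visit average gave 7.6-8.8%.

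**The case against.** The strongest reply is that the sample-size paragraph already ties Pearson's chi-square to the primary outcome, that an unadjusted comparison is valid in a randomised trial, and that the stated size delivers 80% power with it. All of that stands. What it leaves open is that the paragraph says what the size is based on. It does not commit to an analysis, and the analysis table also lists GEE logistic regression.

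It is also fair to say that adjustment is a gain in efficiency whose size depends on an association the documents do not give. At an odds ratio of 3 it is worth only about three points of power. The document also calls the trial a pilot of preliminary efficacy, although section IV.C describes it as a Phase II trial to test efficacy.

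Several stronger readings are tempting but unsupported:

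- **That every listed method is assigned to the primary outcome.** The cell is shared with six intermediate outcomes. A t-test is plausible for visual-analog adherence, and the hazard-ratio calculation is attached to survey variables. T-tests and survival methods are not excluded for suppression, but neither are they assigned to it.
- **That the Cox random effect cannot be identified because each couple contributes one woman.** Nothing says the random effect is the couple, and surveys cover both partners.
- **That a 10-point chance imbalance in baseline suppression amounts to half the 20-point target.** The two are on different scales. At odds ratios of 3 to 20, with 65% suppressed overall, women suppressed at baseline differ from the others by about 0.24 to 0.62 in 24-week risk. Ten points at baseline therefore moves the outcome by about 10 × 0.24 = 2.4 to 10 × 0.62 = 6.2 points. The 5% error rate already allows for such chance differences.

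One uncertainty remains on timing. The Procedures text puts the baseline sample at the group session, while other sections place blood draws at the hospital laboratory. The plan should confirm that the sample precedes allocation.

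**Conclusion.** The concern holds as a gap in pre-specification and a missed efficiency. The plan names no primary analysis of 24-week suppression and gives the baseline viral load no role. Adjustment would raise power from about 80% to between 83% and 92-93% over assumed odds ratios of 3 to 20. Leaving the choice between the two 24-week tests open raises the false-positive rate to about 5-8%, and somewhat further if a GEE over visits is also available.

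A reader might infer that the trial is wrongly sized or that the chi-square is invalid. Neither follows: 89 per arm, 178 and 238 all reproduce, and sizing without baseline information is conservative.

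The results rest on the assumed baseline rates and associations, and on 89 women per arm with both measurements. How the projected 25% loss will be handled in the analysis is a separate matter.

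**What to change.** Before unblinded data are seen, name one primary analysis: logistic regression of 24-week suppression on arm and baseline suppression (below 1,000 copies/mL, yes or no). Report it as a standardised risk difference with a 95% confidence interval, which matches the 0.20 difference used for sizing. Fixing the baseline term as yes/no avoids leaving a second choice open.

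Label the unadjusted chi-square at 24 weeks and the GEE over 6 and 24 weeks as supportive. State that t-tests and survival methods do not apply to viral suppression, which is observed at only three visits, may already be present at baseline and can reverse. Map the remaining methods to the intermediate outcomes they are meant for.

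The cost is SAP wording and minor analysis work. The baseline sample is already planned for every woman, and the sample size need not change.

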Aim 2: Establish the effect of the intervention on intra- and inter-personal mechanisms influencing PMTCT outcomes. *Approach:* I will measure critical intrapersonal factors among female participants (mental health, self-esteem, perceived stigma) and relationship dynamics (IPV, conflict resolution, communication, coping) that are hypothesized to be on the causal pathway between the intervention, PMTCT-related behaviors, and viral suppression. Data will be collected through behavioral surveys at baseline and at 6 weeks and 24 weeks postpartum. I will compare these dynamics between the intervention and control groups and will use mediation analysis and structural equation modeling to test whether these relationship dynamics are affected by the intervention and if they are underlying mechanisms linked to the study outcomes.

II. Background and Significance:

Prevention of mother-to-child transmission (PMTCT) programs have the potential to make substantial gains towards the UNAIDS 90-90-90 goals among pregnant and postpartum women living with HIV (WLWH).¹ However, progress in PMTCT has recently stagnated.⁸ Retention on lifelong antiretroviral therapy (ART), for instance, among pregnant and breastfeeding WLWH in sub-Saharan Africa is far too low; 20% of pregnant women who start ART drop out of care before delivery.⁸ In 2018, it was estimated that 16,000 pediatric HIV infections could have been averted if mothers in Southern Africa were retained on ART (out of 130,000 new pediatric HIV infections that year).⁸ Zambia is one of the countries in Southern Africa with the greatest burden of HIV among women of reproductive age³⁵ and accounts for 3% of the total new global pediatric HIV infections.⁸ In the country, more than 90% of pregnant women attend at least one antenatal care (ANC) visit and receive HIV testing (16% test positive).^{35, 36} Across the additional steps in the PMTCT continuum of care, however, women drop-off at alarming rates (Figure 1).^{3, 20, 21} Even among those who remain engaged in care, optimal viral suppression – a key predictor of mother-to-child transmission (MTCT) and HIV treatment success²²⁻²⁵ – is challenging, especially during the postpartum period.⁷ **Accelerated progress in keeping mothers alive and reducing the incidence of pediatric HIV is dependent on overcoming the critical challenges of ART adherence and sustained retention in care among pregnant and postpartum WLWH.**^{4, 20, 26, 27}

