3. Using a unique adaptive intervention design. Although there is increasing recognition that adaptive intervention designs have significant potential for use in health research,⁴⁷ very few trials have actually examined their effectiveness in promoting health outcomes and even fewer, have been applied to HIV.⁴⁸ Adaptive approaches use the dynamics of the “system” of interest (e.g., the couple) via a sequence of decision rules and tailoring variables to determine when and how the intervention should be modified to optimize effectiveness.⁴⁷ I propose to adapt specific intervention content delivered based on baseline data related to engagement in HIV care and relationship dynamics using pre-established guidelines. For instance, couples that report IPV will receive increased training in conflict negotiation skills. This adaptive approach has the potential to better meet the needs of heterogeneous couples participating in the intervention.

III. Preliminary Studies/Progress Report:

Refining a couples counseling intervention for pregnant WLWH and their male partners (K99 phase): To inform the content and delivery of the proposed R00 intervention, in Years 1-2 of the K99/R00, I conducted qualitative interviews with pregnant WLWH (n=30) and their male partners (n=18) in the target community. We also held three focus group discussions with service providers (lay health workers and community leaders; n=27). We asked participants to do a pile sorting activity prioritizing specific relationship skills they would want in a couples-based intervention, additional desired health and relationship content, and delivering the intervention in acceptable ways. This project provided key data on ways to ensure that the intervention will be acceptable and feasible in the community, and subsequently, have the greatest likelihood of efficacy. It also highlights my ability to conduct research in this setting with the target population (pregnant WLWH and their male partners).

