Data-related risk reporting and action plan: We will closely track incoming numbers of participants via ongoing recruitment activities, and weekly and monthly progress reports will be compiled by the study staff and reviewed by the Study Coordinator and the PI. We will utilize similar procedures to monitor any missing data. Recruitment and missing data reports will be monitored weekly by the Study Coordinator and monthly by the PI. All data will be protected on firewall-protected servers at the University of Colorado. Any identification of recruitment rates or follow-up rates that represent threats to our ability to sufficiently answer the research questions will be met with action by the PI to intervene to remedy the shortcomings, including adding additional recruitment sites (antenatal clinics). Should a situation arise of insufficient power or early detection of research questions, the PI will review and discuss with NIMH halting the study, when and if needed, and would report such action to all monitoring bodies. Completion rates of intervention activities will be monitored in parallel fashion using study logs.

Safety-related risks: Safety-related risks to participants could consist of: 1) emotional discomfort or distress resulting from sensitive questions being asked on the behavioral questionnaires pertaining to HIV and/or relationship issues; 2) social risk (e.g. risk to reputation) if confidential information revealed during the course of the study were to be disclosed outside of the research team; 3) tension, conflict or violence between the partners 4) risks related to biospecimen collection (research-only blood draws), such as physical discomfort, and the unlikely potential for infection or other physical repercussions from

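### Violence between partners is a named safety risk with no harm analysis by arm; the one planned comparison, of past-month IPV overall, can understate or hide new or worsening violence

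*Combined protocol and SAP*

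**What the plan says.** - **Risk.** IV.D, under safety-related risks, includes "tension, conflict or violence between the partners".
- **Who is enrolled.** IV.B requires "no severe IPV in the past 6 months". Women with less severe or earlier violence and women with none are both eligible.
- **What the intervention does about IPV.** Section II, item 3, says that "couples that report IPV will receive increased training in conflict negotiation skills". In the IV.C component table, counselling visit 2, which all intervention couples receive, also covers settling conflict without violence.
- **Measurement.** Both arms are surveyed at baseline, 6 weeks and 24 weeks postpartum. IV.F.1 names the Revised Conflict Tactics Scale among the source instruments. The baseline survey takes place at the first group session, and randomisation follows that session.
- **Analysis.** In the IV.F.1 table IPV appears only as "IPV past month" among the Aim 2 interpersonal mechanisms, with the method "Mediation analysis with structural equation modeling". Aim 2 in Section I adds: "I will compare these dynamics between the intervention and control groups". Whether IPV is scored as any/none, as a frequency or as a scale is not stated.
- **Safety handling.** IV.D provides a local safety manager who monitors data and events and follows up reported IPV, response protocols for relationship harms, adverse event reporting, and monthly review of the study data by the investigator. None of these is described as a comparison of the arms.

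**The concern.** The planned use of IPV suits a question about benefit: does average violence fall, and does that carry the effect on viral suppression? It does not suit a question about harm. Joint counselling could reduce violence in some couples and provoke it in others, and an overall comparison adds the two changes together. The design makes such opposing changes plausible, because couples who already report IPV receive added conflict content, while a first report of IPV can only come from women who did not report it at baseline. Adjusting for baseline IPV in a regression or SEM would still return one averaged effect. If IPV is scored any/none, worsening among women who already report it is invisible; if it is a score, worsening and improvement average out.

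At stake is a report of no difference in IPV, or of a benefit, that leaves unanswered whether violence began or worsened more often in counselled couples. Section IV.G says the results will support a larger trial, so the gap would carry forward.

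**Working it through.** **1. The plan's own figure.** Inputs from IV.F.2: 55% against 75%, power 0.80, alpha 0.05 (taken as two-sided), 25% loss.

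n per arm = [1.96·√(2·0.65·0.35) + 0.842·√(0.55·0.45 + 0.75·0.25)]² / 0.20² ≈ 88.1, rounded up to 89, so 178 in total. 89 / 0.75 = 118.7, so 119 per arm and 238 in total. Both stated figures reproduce. The documents give no sample size figure for IPV itself, so 89 women per arm is carried forward.

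**2. What the overall comparison measures.** Let b be baseline IPV, p persistence among women with it, and q onset among women without it. End-line IPV in an arm = b·p + (1 − b)·q.

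The documents give none of these for this trial. Assumed: control p = 60% and q = 10%; intervention q = 20%; b from 20% to 60%; loss unrelated to IPV.

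**3. When a doubling of onset is fully masked.** Net IPV is equal when intervention p = [b·0.60 + (1 − b)·0.10 − (1 − b)·0.20] / b. At b = 40%: (0.24 + 0.06 − 0.12) / 0.40 = 45%. For onset in women without baseline IPV, m = 89·(1 − b), and the 95% half-width on the difference is 1.96·√[(0.10·0.90 + 0.20·0.80)/m].

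| Baseline IPV | Net IPV, both arms | Intervention persistence that masks it | Women per arm without baseline IPV | New reports, control / intervention | Power, 10% vs 20% | Half-width, points |
|---|---|---|---|---|---|---|
| 20% | 20% | 20% | 71 | 7.1 / 14.2 | 39% | 12 |
| 30% | 25% | 37% | 62 | 6.2 / 12.5 | 34% | 12 |
| 40% | 30% | 45% | 53 | 5.3 / 10.7 | 30% | 13 |
| 50% | 35% | 50% | 45 | 4.5 / 8.9 | 26% | 15 |
| 60% | 40% | 53% | 36 | 3.6 / 7.1 | 22% | 16 |

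**4. Masking is not automatic.** If persistence falls from 60% to 40% and onset doubles, the net difference (intervention minus control) is 0.10·(1 − b) − 0.20·b = 0.10 − 0.30·b: +4 points at b = 20%, +1 at 30%, −2 at 40%, −5 at 50% and −8 at 60%. At low baseline IPV the overall comparison leans towards harm; at higher levels it favours the intervention although onset has doubled.

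**5. Recall window.** Taking a month as about four weeks, past-month items at 6 and 24 weeks cover roughly weeks 2–6 and 20–24. Weeks 6–20, with the counselling visits at 12 and 18 weeks (IV.C), fall outside the analysed variable.

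**6. Missing data.** The plan projects 119 − 89 = 30 women lost per arm, of whom 0.10 × 119 ≈ 12 through break-ups. That exceeds the number of new reports in most rows above, and a break-up may itself follow violence.

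**The case against.** **Violence is monitored.** This stands. IV.D provides individual follow-up and also study-level review, with protections reassessed if increased risk is found. A reader might infer that violence would go unnoticed; the documents do not support that. But where IPV is common, case reports cannot show an excess due to counselling. A comparison by arm can, and none is planned.

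**The background rate is over 60%, so cancellation is likely.** A reader might infer this, but Section II and the preliminary studies take that figure from an earlier study with no recall window given. This trial excludes recent severe IPV and analyses the past month, so its baseline may be lower. The level matters. With control rates as above, and intervention persistence of 50% and onset of 25%, net IPV is 20% against 30% at a 20% baseline and 30% against 35% at a 40% baseline, which points to harm; it cancels only at 60%.

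**Any severe report at follow-up is an escalation.** This does not follow either. The exclusion looks back only 6 months, so a later report may be a recurrence. Likewise, no report in the past month at baseline does not mean no earlier IPV.

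**Benefit and harm do not divide neatly by baseline IPV.** This stands. Visit 2 could prevent violence in women without baseline IPV, and women with it could get worse. The harms table therefore needs to cover both groups.

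**The hazard-ratio sentence in IV.F.2 implies a time-to-event analysis of IPV.** No IPV event or at-risk set is defined, and the Aim 2 row lists only mediation with SEM. A hazard ratio of 0.75 also needs about 4·(1.96 + 0.842)² / (ln 0.75)² ≈ 380 events, against at most 238 enrolled women with one first event each.

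**Net averages can hide subgroup effects for any outcome, and this is a pilot.** This is fair, and it limits the weight of the point. Here, though, the hidden direction is a harm that the protocol itself names.

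**Conclusion.** The point holds as a gap in the planned analysis of harm. Partner violence is a named risk measured in both arms at three times, yet the only planned analysis by arm is an overall comparison of past-month IPV alongside its use as a mediator. That comparison can hide a doubling of onset at every baseline level tried from 20% to 60%, provided persistence falls enough: to 20% at the lowest level and to 53% at the highest.

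The persistence, onset and baseline rates are assumptions. Nothing in the documents shows that counselling will provoke violence, or that the overall comparison will come out null. The Aim 2 analysis is not invalid for its own purpose. This is a cheap improvement that should be made, and what it yields is an estimate with a wide interval, not a powered test.

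**What to change.** Add to IV.F a descriptive harms table by randomised arm, separate from the Aim 2 mediator analysis and based on women's survey responses and the event reports already planned:

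- (a) percent reporting IPV at 6 or 24 weeks among women reporting no past-month IPV at baseline, labelled new or recurrent;
- (b) percent with worsening on the collected IPV scale among women with baseline IPV, with the scoring and the meaning of worsening fixed in advance;
- (c) percent with severe IPV at 6 or 24 weeks among all women, using the severity definition applied at screening, which the SAP should write out because the protocol does not;
- (d) partner-violence adverse events by arm.

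Give risk differences with 95% confidence intervals. Show missing surveys and break-ups by arm beside them. State that past-month recall leaves roughly weeks 6–20 uncovered. Because the baseline survey precedes randomisation, (a) and (b) compare groups defined before allocation.

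The cost is SAP wording and one table; no new data, visits, sample size or clinical rule is needed. The downside is imprecision: about 36 to 71 women per arm in (a), half-widths of about 12 to 16 points, and power of 22% to 39% for 10% against 20%. The text should say that the absence of a clear difference is not evidence of safety.
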